Medication (nitrofurantoin or placebo) will be self-administered by the patient once daily beginning on postoperative day one and continuing each day the patient requires catheterization. Patients who must take a study drug while under hospital care will self-administer study drug with a physician order that they may do so, and under supervision of the nursing staff, or per hospital protocol of participating institutions.

Patients using indwelling catheters will be seen for repeat voiding trial at the discretion of the treating provider. All women will be asked to complete a simple daily diary for each day they use a catheter to document compliance with study drug, symptoms of UTI, or adverse effects from study drug (see Daily Diary). Criteria for discontinuing indwelling catheter use will be passing a voiding trial per policy of participating sites. Criteria for discontinuing CISC will per policy of participating sites. At our institution, patients may discontinue CISC when they are able to void spontaneously with a PVR of less than 100cc on two consecutive voids, and this will be the preferred criteria. Patients will return the diary by mail in pre-addressed envelopes when they discontinue catheter use.

Patients will be strongly encouraged to seek care for possible UTI symptoms from their study physician. A symptom survey and urine specimen for culture will be collected. Catheterized specimens are preferred although clean catch specimens will be accepted. UTI symptoms will be treated with antibiotics (other than Nitrofurantoin) at the discretion of the treating physician; type, duration and strength of antibiotic will be recorded. When symptoms occur outside of business hours, patients may reach an on-call study staff member who can help them facilitate urine culture collection as well as clinical care. Empiric prescription of antibiotics prior to obtaining urine for culture will be strongly discouraged. Patients will be given a prescription and specimen cup for a urine culture so they can drop off a specimen if empiric treatment is necessary. They will also be given a card identifying them as study participants with a request to send a urine culture and to forward results to their physician should they present for care to an outside facility.

An episode of UTI symptoms will only be considered a UTI if confirmed by a positive urine culture, as defined below. If empiric treatment occurs, the episode will be counted as a UTI.

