Primary outcome: The frequency of urinary tract infection within 6 weeks of surgery will be analyzed by intention to treat using a chi squared test. This primary outcome includes symptomatic, culture-proven UTI as well as women who were empirically treated outside of protocol. Women who were diagnosed with multiple urinary tract infections during the study period will be counted, but only the first UTI for each patient will be included. A secondary analysis of symptomatic, culture-proven UTIs, excluding those who were empirically treated, will be performed by chi square test. In addition, frequency of urinary tract infection among women undergoing urinary incontinence (UI) surgery only, pelvic organ prolapse (POP) surgery only, or a combination of UI/POP surgeries will be performed using chi squared or Fisher's Exact test as appropriate.

Secondary outcomes:

1. Frequency of adverse events related to daily nitrofurantoin exposure as defined above will be compared with chi-squared test or Fisher's Exact test as appropriate.
2. Frequency of urine cultures positive for nitrofurantoin-resistant isolates will be analyzed by chi-squared test or Fisher's Exact test as appropriate.

PROJECT SCHEDULE:

- February 8, 2016: Final confirmation of participating sites
- February 8 to April 4, 2016: Start up including IRB approval at all sites
- April 2016 until April 2017: Recruitment
- May through July 2017: Data analysis, manuscript completion

REFERENCES

[name] & [name]. RCT of nitrofurantoin prophylaxis during short-term postop catheterization.

Dieter AA1, Amundsen CL, Edenfield AL, Kawasaki A, Levin PJ, Visco AG, Siddiqui NY. Oral antibiotics to prevent postoperative urinary tract infection: a randomized controlled trial. *Obstet Gynecol*. 2014 Jan;123(1):96-103.

Guay DR. An update on the role of nitrofurans in the management of urinary tract infections. *Drugs* 2001;61:353-64.

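### The secondary culture-confirmed analysis excludes empirically treated cases without saying whether women or episodes are removed, and on either reading it ignores cultures that the protocol arranges

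*Combined protocol and SAP*

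**What the plan says.** Under Study Design, the primary outcome is defined as UTI symptoms or signs together with a urine culture above a stated threshold, within 6 weeks of surgery.

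The Data Analysis section then widens the outcome that is tested. The primary comparison is by intention to treat ("The frequency of urinary tract infection within 6 weeks of surgery will be analyzed by intention to treat using a chi squared test"), and "This primary outcome includes symptomatic, culture-proven UTI as well as women who were empirically treated outside of protocol". Protocol in Detail agrees: "If empiric treatment occurs, the episode will be counted as a UTI".

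The culture-confirmed outcome on its own is left to a secondary comparison: "A secondary analysis of symptomatic, culture-proven UTIs, excluding those who were empirically treated, will be performed by chi square test". No analysis set or denominator is given for it; the intention-to-treat statement is attached only to the primary comparison.

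Protocol in Detail also plans for cultures when treatment is empiric. "Empiric prescription of antibiotics prior to obtaining urine for culture will be strongly discouraged", but "Patients will be given a prescription and specimen cup for a urine culture so they can drop off a specimen if empiric treatment is necessary". For care sought elsewhere, "They will also be given a card identifying them as study participants with a request to send a urine culture", with results to be forwarded.

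**The concern.** Empiric treatment happens after randomisation and is prompted by UTI symptoms, which are one of the two parts of the endpoint. An exclusion based on it is therefore tied to the outcome. The sentence can be read in two ways, and each has a cost.

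- **Women are removed.** This is the more natural reading, because the same paragraph has just spoken of women treated empirically. The denominators are then no longer the randomised ones, and if nitrofurantoin works, more women are expected to leave the placebo arm.
- **Episodes are removed.** The denominators stay intact, but a woman with symptoms and a qualifying culture is scored as having no UTI because antibiotics were started before the result.

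On both readings, any culture obtained from these women is ignored. The primary analysis counts empiric treatment as an event, so this secondary analysis is the only planned overall comparison that follows the endpoint definition under Study Design. A reader would use it to check whether the composite primary result also holds for confirmed infection.

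**Working it through.** **The plan's own figure.** Power Analysis gives 33% v 13%, two-sided alpha 0.05, 80% power, 69 per arm, and 77 per arm after 10% dropout. With pooled variance and mean rate 0.23:

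n = [1.96 × √(2 × 0.23 × 0.77) + 0.842 × √(0.33 × 0.67 + 0.13 × 0.87)]² / 0.20² = 68.3, so 69 per arm; 69 / 0.90 = 76.7, so 77 per arm and 154 in total.

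The stated figure reproduces. Power at 69 per arm is 80.4% by the normal approximation and 81.5% by exact enumeration of the uncorrected chi-squared test. The exact value is used below.

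**Assumptions not in the documents.** Let p be the culture-confirmed rate (0.33 or 0.13, from Power Analysis). Let c = 0.10 be the share of women without UTI who have culture-negative symptoms. Let e be the share of symptomatic episodes treated empirically, taken as 5% to 30%. Both c and e are assumed equal in the two arms.

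**If women are removed.** Excluded share X = p·e + (1 − p)·c·e. Rate among those left r = p(1 − e) / (1 − X). At e = 0.20:

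- Placebo: X = 0.066 + 0.0134 = 7.9%; r = 0.264 / 0.9206 = 28.7%.
- Nitrofurantoin: X = 0.026 + 0.0174 = 4.3%; r = 0.104 / 0.9566 = 10.9%.
- Of 77 per arm, about 6 v 3 women are lost.

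| e | Excluded, placebo v active | Rates among those left | Difference (points) | Power from 69 per arm |
|---|---|---|---|---|
| 0 | 0 v 0 | 33% v 13% | 20.0 | 81.5% |
| 5% | 2.0% v 1.1% | 32.0% v 12.5% | 19.5 | 79.8% |
| 10% | 4.0% v 2.2% | 30.9% v 12.0% | 19.0 | 78.1% |
| 20% | 7.9% v 4.3% | 28.7% v 10.9% | 17.8 | 73.7% |
| 30% | 11.9% v 6.5% | 26.2% v 9.7% | 16.5 | 69.8% |

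**Relative measures.** The odds among those left are p(1 − e) / [(1 − p)(1 − c·e)]. The factor (1 − e) / (1 − c·e) is the same in both arms and cancels, so the odds ratio stays at 0.303 throughout. The risk ratio moves slightly away from 1, from 0.394 to 0.379 at e = 20%.

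**Type I error.** With equal UTI rates and equal empiric treatment in both arms, expected losses are equal. Simulation at 77 per arm, with UTI rates of 13%, 23% and 33% and with 20% or 50% of UTIs treated empirically, gave 4.9% to 5.1%.

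**If episodes are removed and the women stay as non-events.** The rate is p(1 − e) and the difference is 0.20 × (1 − e). At e = 20% this is 26.4% v 10.4%, or 16.0 points, with 69.5% power at 69 per arm. The risk ratio stays at 0.394.

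**What using the cultures would recover, at e = 20%.**

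- All empirically treated UTIs confirmed by culture: 20 points and 81.5% power.
- Half confirmed, the rest scored as non-events: 0.33 × 0.90 = 29.7% v 0.13 × 0.90 = 11.7%, or 18.0 points, with 76.0% power.
- None cultured, all scored as non-events: 16.0 points and 69.5% power, which is worse than removing the women.
- None cultured, all scored as events: 0.33 + 0.67 × 0.10 × 0.20 = 34.3% v 0.13 + 0.87 × 0.10 × 0.20 = 14.7%, or 19.6 points.

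The last two lines show why a missing culture must be kept apart from a negative one.

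**The case against.** Much of the case on the other side stands.

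- **Wording.** The excluded items can grammatically be the UTIs rather than the women. A reader might infer that the randomised comparison is certainly broken and that women are certainly lost unequally. The text does not settle that. Unequal loss is an expectation that requires the arms to differ in UTI rate and empiric treatment to follow symptoms.
- **Scope of the exclusion.** Data Analysis describes the empiric treatment as outside of protocol. That could mean women treated with no culture at all, in which case no result is discarded. Protocol in Detail provides a route to a culture but does not guarantee one.
- **Bias.** A reader might infer that the analysis is invalid or prone to false positives. Under the assumptions used here the odds ratio does not move and type I error stays near 5%. The trial is double-blind, so empiric treatment driven by known allocation is unlikely. What changes is the absolute rates, the risk difference and the power.
- **Size.** Empiric treatment is strongly discouraged and its frequency is not given. At 5% the effect is negligible.
- **Reach.** The primary analysis keeps these women and counts them as events, and the sample size was not set for this secondary comparison. An inference that the main result is compromised has no support.

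These points limit the size of the concern but do not remove it. The denominator is unstated, and each reading either drops randomised women or miscounts confirmed infections wherever a culture exists.

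**Conclusion.** The point holds as a defect in a secondary analysis that should be corrected. The rule is ambiguous, is tied to a symptom-driven event after randomisation, and leaves unused the culture results that the protocol tries to obtain.

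Its size cannot be fixed from the documents. With the arms at 33% and 13%, 5% to 30% of symptomatic episodes treated empirically, and culture-negative symptoms in 10% of women without UTI, removing the women lowers the risk difference by 0.5 to 3.5 points and power at 69 per arm by about 2 to 12 percentage points. The odds ratio result depends on empiric treatment following symptoms in the same way in both arms.

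**What to change.** Replace the exclusion in Data Analysis with wording such as:

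> All randomised women remain in the denominator. A woman is an event if she had symptoms and any culture meeting the primary outcome definition under Study Design, whether or not antibiotics were started empirically. Empirically treated women with a negative culture are non-events. Empirically treated women with no culture are treated as missing, and results are shown with them counted first as non-events and then as events in both arms.

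This takes a few sentences in one section and no new data collection, because Protocol in Detail already arranges the cultures. The small downside is that two bounds are reported in place of one figure. They will be close if most empirically treated women have a culture, and wider if few do.

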Secondary Aim(s): To determine how nitrofurantoin antibiotic prophylaxis administered to patients using an indwelling catheter or CISC after pelvic organ prolapse and/or urinary incontinence surgery affects frequency of adverse events related to daily nitrofurantoin exposure, and frequency of urine cultures positive for nitrofurantoin-resistant isolates.

The Null Hypotheses: Nitrofurantoin antibiotic prophylaxis administered to patients using an indwelling catheter or CISC after pelvic organ prolapse and/or urinary incontinence surgery does not change the incidence of symptomatic and culture proven urinary tract infection (UTI) compared with placebo.

BACKGROUND

Urinary tract infections (UTI) occur frequently following surgery for urinary incontinence or pelvic organ prolapse (POP), with reported incidence up to 48% (Albo 2007, Chai 2009, [name] 2010, Nygaard 2011, Wei 2012). This high rate is frequently attributed to intraoperative factors, such as manipulation of the genitourinary tract and instrumentation of the bladder and urethra, as well as an approximately 50% rate of short

term postoperative catheterization following urogynecologic surgery ([name] 2010, Nygaard 2010, Dieter 2014). As American women have a 20% lifetime risk of surgery for POP or urinary incontinence, the absolute number of women at risk for urinary infectious morbidity associated with these procedures is quite high (Wu 2014).

The substantial risk of UTI following POP or incontinence surgery, combined with the well-established risk associated with catheterization, leads many practitioners to prescribe oral antibiotics to women undergoing catheterization in the postoperative period. However, there is minimal Level I evidence to support or refute this practice. The Infectious Disease Society of America (IDSA) Guideline acknowledges that prophylactic antibiotics have been shown to reduce UTI rates among patients using short term postoperative catheterization in randomized trials (Hooton 2009). However, they recommend against routine antibiotic prophylaxis use due to concerns regarding antimicrobial resistance, cost, and potential for adverse effects, even among high risk groups including women undergoing urogynecologic surgery. This recommendation is based on expert opinion, given a paucity of trial data to guide clinical care.

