Nitrofurantoin is a commonly used antibiotic for UTI prophylaxis during catheterization, is well-tolerated with few adverse effects, and is known to have a very low rate of associated resistance (Shaw 1989). After decades of use, it remains active against the most common UTI pathogens that have gained resistance to other antimicrobials (Guay 2001). For example, in the 2013 Magee-Womens Hospital Adult Antibigram, 98% of E-coli specimens were sensitive to Nitrofurantoin, which has been consistent since at least 2007. The drug has a half-life of 20 minutes and 40% is concentrated in and excreted into the urine in a therapeutically unchanged form. Thus it has minimal impact on vaginal and bowel flora. Nitrofurantoin has been shown to reduce the incidence of positive urine cultures and symptomatic UTIs in women with a suprapubic catheter after pelvic organ prolapse and/or urinary incontinence surgery (Rogers 2004). No trials have evaluated nitrofurantoin prophylaxis for women using short term indwelling catheters or CISC following urogynecologic procedures.

[figure not shown]
Given the large number of women at risk for urinary infectious morbidity associated with short term catheterization for acute urinary retention following POP and/or incontinence surgery, and the paucity of data on the impact of antibiotic prophylaxis in this setting, we propose to demonstrate the efficacy of nitrofurantoin prophylaxis through an adequately-powered, placebo-controlled trial. Secondary outcomes will include adverse events associated with nitrofurantoin use, and incidence of nitrofurantoin resistant bacterial isolates from urine culture.

SIGNIFICANCE

This prospective, randomized control study is uniquely feasible in the Fellows' Research Pelvic Network, where data from a large and diverse patient population can be collected.

STUDY DESIGN

Women who undergo surgery for urinary incontinence and/or pelvic organ prolapse who fail a post-operative voiding trial will be eligible to participate in this a double blind, randomized trial. Randomization will be a block randomization stratified by site with 1:1 allocation to either extended release nitrofurantoin 100mg or an identical appearing placebo capsule to be taken daily while using an indwelling catheter or performing CISC. Neither the patient, nor her physician nor the research staff will know her allocation. The diagram below outlines randomization details:

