Participants will be assigned a Study ID number at study enrollment. Study ID number will be taken from the randomization log provided to the participating sites. This Study ID number should be used label all data collection sheets. All communication between the DCC and participating sites regarding patient data will occur via the Subject ID number. The staff at the DCC will not have access to any identifying information available to the participating site. The DCC staff will have access to the Subject ID number for data management purposes. Once a Subject ID number has been assigned, it should never, for any reason, be reassigned.

The DCC will maintain the randomization log. They will maintain a record of the block randomization including which Study ID numbers have been assigned to which clinical site. Only the onsite pharmacy or other research staff personnel for each clinical site will maintain patient identifiers associated with the Study ID number. This information must be kept in a secure area in accordance with each site's IRB policy and approval.

POWER ANALYSIS

In a study by Rogers et al, the rate of UTIs with placebo in women with suprapubic catheters was 33%. In a study at Magee Womens Hospital, 13% of those performing CISC post-operatively developed a symptomatic UTI, despite daily prophylactic nitrofurantoin ([name], 2010). Assuming a 60% decrease attributable to nitrofurantoin from 33% to 13%, with 80% power and a two-sided alpha of 0.05, we will need 69 patients per arm. Allowing for a 10% dropout rate, we will recruit a total of 154 patients, 77 per arm.

DATA ANALYSIS

Demographics and baseline data will be analyzed by Student's t-test and chi-squared test or Fisher's Exact test as appropriate.

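### The surgery-type UTI analysis does not name its comparison and has no treatment-by-type test, so within-type p-values could not show whether the effect differs by type

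*Combined protocol and SAP*

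**What the plan says.** The surgery-type analysis is the last item in the primary-outcome paragraph of Data Analysis. It covers "frequency of urinary tract infection among women undergoing urinary incontinence (UI) surgery only, pelvic organ prolapse (POP) surgery only, or a combination", and the method is given as a combination "of UI/POP surgeries will be performed using chi squared or Fisher's Exact test as appropriate". The sentence names three groups and a test. It does not say whether the arms are compared within each group or the groups are compared with one another. No section mentions an interaction term, a homogeneity test or a model.

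Four other statements give the context:

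- The primary outcome "will be analyzed by intention to treat using a chi squared test".
- Power Analysis sizes that overall comparison only: "from 33% to 13%, with 80% power and a two-sided alpha of 0.05, we will need 69 patients per arm".
- Study Design: "Randomization will be a block randomization stratified by site with 1:1 allocation". Surgery type is not a stratification factor.
- Specific Aims lists as secondary questions how prophylaxis "affects frequency of adverse events related to daily nitrofurantoin exposure, and frequency of urine cultures positive for nitrofurantoin-resistant isolates". Effect by surgery type is not among them.

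**The concern.** Readers of a table by surgery type will want to know whether the drug works better after one kind of surgery than another. Separate tests within types do not answer that. A p-value below 0.05 in one type and above it in another can come from a single common effect observed in groups of different size, or from chance. The test that addresses the question compares the three treatment effects with each other, and the plan has none.

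If the sentence means a comparison of UTI frequency across the three types, it would describe how risk varies with surgery and say nothing about treatment effect by type. The gap is there on both readings. The figures below apply only to the within-type reading. What is at stake is a misleading statement about surgery type in the report.

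**Working it through.** **Inputs.** From Power Analysis: 33% on placebo, 13% on nitrofurantoin, two-sided alpha 0.05, 80% power, 69 evaluable per arm. The surgery mix is not in the documents, so five splits of 69 per arm are assumed. Arms are taken as equal within each type, and the placebo rate as 33% in every type.

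**The plan's own figure.** n = [1.960·√(2·0.23·0.77) + 0.8416·√(0.33·0.67 + 0.13·0.87)]² / 0.20² = (1.1665 + 0.4865)² / 0.04 = 68.3, so 69 per arm. With 10% dropout, 69/0.9 = 76.7, so 77 per arm and 154 in total. The stated size reproduces, for the overall comparison.

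**Within-type power and mixed patterns.** Power in each type is found by enumerating all pairs of binomial counts. With powers p1, p2, p3, a mixed pattern (at least one type significant and at least one not) has probability 1 − p1·p2·p3 − (1−p1)(1−p2)(1−p3). For equal thirds by chi-squared this is 1 − 0.375³ − 0.625³ = 0.70.

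| Women per arm in the three types | Power in each type, chi-squared | Power in each type, Fisher | Mixed, chi-squared | Mixed, Fisher |
|---|---|---|---|---|
| 23 / 23 / 23 | 0.375 in each | 0.266 in each | 0.703 | 0.586 |
| 14 / 28 / 27 | 0.238, 0.426, 0.445 | 0.132, 0.310, 0.290 | 0.712 | 0.563 |
| 10 / 35 / 24 | 0.140, 0.514, 0.393 | 0.059, 0.412, 0.284 | 0.718 | 0.597 |
| 7 / 48 / 14 | 0.082, 0.660, 0.238 | 0.019, 0.567, 0.132 | 0.749 | 0.630 |
| 14 / 41 / 14 | 0.238, 0.594, 0.238 | 0.132, 0.500, 0.132 | 0.731 | 0.615 |

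The true effect is the same in every type in every row.

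**Smaller effects.** Over the same five splits:

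| Drug rate | Mixed, chi-squared | Mixed, Fisher | None significant, chi-squared | None significant, Fisher |
|---|---|---|---|---|
| 18% | 50–52% | 35–37% | 47–50% | 63–65% |
| 20% | 41–43% | 27–29% | 56–59% | 71–73% |

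At 20%, no significant type is the commonest result with either test. With Fisher's test that is already so at 18%.

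**What intervals would show.** Newcombe 95% CIs for one type's risk difference, placebo minus drug, for illustrative counts:

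- 8/23 vs 3/23: 22 points (−3 to 44)
- 2/7 vs 1/7: 14 points (−28 to 52)
- 16/48 vs 6/48: 21 points (4 to 36)

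The three estimates are similar and the intervals overlap widely, yet only the last excludes zero.

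**Behaviour of a heterogeneity test.**

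- *Zero-event cells.* The chance that some arm of some type has no events is 1 − ∏(1 − 0.87ⁿ)(1 − 0.67ⁿ): 12%, 18%, 29%, 50% and 27% in the order of the first table. At a drug rate of 20% the range falls to 2–29%. Wald tests from ordinary logistic regression are unreliable in such tables.
- *Rejection under a uniform effect, nominal 5%.* By simulation, the 2-df logistic likelihood-ratio test rejects in 6.8–7.5% of trials (200,000 per setting) and an exact test of homogeneity of odds ratios in 3.7–4.5% (20,000 per setting).
- *Power when the drug rate is 13% in some types and 33% in the others.* Equal thirds: 19–21% exact, 24–27% likelihood-ratio. Uneven splits: 8–24% exact, 14–29% likelihood-ratio.

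**Scale.** The planned odds ratio is (0.13/0.87)/(0.33/0.67) = 0.303. Holding it constant, an assumed placebo rate of 20% gives a drug rate of 7.0% (13 points difference), 33% gives 13% (20 points), and 45% gives 19.9% (25 points). If baseline risk differs by type, equal odds ratios therefore mean unequal risk differences.

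**The case against.** The strongest reply is that this is a supplementary analysis answering a question the protocol never poses. Its wording already places it after the main analyses, and the text states no inference to be drawn from a mixed pattern. The within-type reading is inferred, and without it the mixed-pattern figures do not arise. The proposed heterogeneity test would usually miss a real difference. All of this stands. It is why the rating is low, why the first request is to name the comparison, and why estimates with intervals come ahead of any test.

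Three stronger inferences are tempting, and the documents do not support them.

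- *A stated objective goes untested.* Effect by surgery type appears neither in Specific Aims nor among the secondary outcomes.
- *Site-only stratification is what leaves the group sizes uncontrolled.* Stratifying by surgery type would not fix them either; only enrolment quotas would. What site-only stratification allows is imbalance between arms within a type, and the calculations above do not include that.
- *The reader is left with nothing by which to judge a mixed pattern.* If frequencies are reported by arm within type, each risk difference, its interval and a homogeneity test can be derived from the table, and the overall result is also there. The plan omits the right summary, but it does not withhold the information.

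**Conclusion.** The concern holds as a minor one. The comparison is not named, and on neither reading does the plan test whether the treatment effect differs by surgery type. On the within-type reading, a mix of significant and non-significant types is the usual result of a uniform effect at the plan's own rates: 56–75% over the five splits. It remains common at smaller effects, 35–52% at a drug rate of 18% and 27–43% at 20%.

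These sizes rest on assumed surgery mixes, equal arms within type and one placebo rate throughout. That within-type p-values are not a test of difference depends on none of these assumptions.

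**What to change.** In Data Analysis:

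1. State that the comparison is nitrofurantoin against placebo within each surgery type, if the authors confirm that this is meant.
2. Make each type's effect estimate with a 95% CI the main output, in place of within-type p-values.
3. Add one 2-df treatment-by-surgery-type heterogeneity test that copes with zero-event cells, such as an exact test of homogeneity of odds ratios. Avoid Wald tests. A likelihood-ratio test is usable but somewhat liberal.
4. Name the scale of that test, and report odds ratios beside the risk differences.
5. Label the analysis exploratory.

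The cost is a few sentences. Surgery type is already needed for the planned analysis, so there are no new data and no change in sample size. The drawback is low power, so the text should add that a non-significant heterogeneity test does not show a uniform effect.
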